1.3 Schedule of Assessments

Tests and procedures	Pre-reg	≤14 days prior to start of therapy	Initial 4 weeks of progesterone therapy				Second 4 weeks of progesterone therapy	Subsequent maintenance progesterone therapy
			d1	d8	d15	d22	d29	Beginning of every 4 week interval to study end (up to 24 wks of therapy) ¹⁰
Informed consent	X							
Path diagnosis	X							
H&P, KPS		X ⁴			X ⁵		X ⁵	X ⁶
Height (only initially), Weight		X			X ⁵		X ⁵	X ⁶
Neuro assessment		X			X ⁵		X ⁵	X ⁶
Adverse event assessment			X	X ⁵	X ⁵	X ⁵	X ⁵	X ⁶
Medical History	X							
Concomitant medication	X	X	X	X ⁵	X ⁵	X ⁵	X ⁵	X ⁶
Initial Consult	X ³							
CBC w/diff		X					X ⁵	X ⁶
CMP ¹		X					X ⁵	X ⁶
Exploratory serum biomarkers		X					X ⁵	
Pharmacokinetic assessment			X ⁸	X ⁸				
MRI w/ & w/o contrast ²		X					X ⁵	X ⁷
Steroid/anti-Sz med documentation		X	X	X ⁵	X ⁵	X ⁵	X ⁵	X ⁶
QOL assessments		X					X ⁵	X ⁹
Pregnancy test		X ¹¹						
Drug diary documentation			X ¹²		X ¹²		X ¹²	X ¹²

Note – AE assessments, concomitant medications and steroid/anti-Sz med documentation at d8 and d22 may be done by telephone, if the patient does not otherwise need to be seen in clinic.

¹ Comprehensive Metabolic Panel (CMP) - Sodium, potassium, bicarbonate, chloride, BUN, creatinine, calcium, glucose, total bilirubin, SGOT (AST), SGPT (ALT), alkaline phosphatase, albumin, total protein (Standard care). The frequency of CMP will be up to the treating physician's discretion.

² Standard diagnostic brain MRI w/ & w/o contrast.

³ Initial consultation by either neuro-oncology or radiation oncology can be completed ≤ 21 days before initiation of therapy.

⁴ May be satisfied by H&P at initial consultation if within 14 days of starting therapy.

⁵ May be assessed ± 3 days.

⁶ May be assessed ± 7 days. Final followup (including AE assessment) will be at 28 days after last drug dose.

⁷ To be assessed after 8 weeks of therapy ± 1 week and then every 8 weeks ± 2 weeks, thereafter. Other MRIs can be done at discretion of treating physician, if needed.

- ⁸ To be performed on day 1 (0, 30 minutes, 1, 2, 4, 6, 8 hrs from drug injection) as well as at day 8 prior to drug injections on those days only in patients getting PK evaluations. (May alternatively be done on any day after the 1st week during the initial 4 weeks with no need for day 8 trough draw if done later)

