- Brief medical history, symptom-directed physical exam including KPS and neurologic assessment (on day 15, on day 29, every 4 weeks thereafter). Can be performed at ± 3 days during first 8 weeks and ± 7 days thereafter.
- Vitals signs, weight (on day 15, on day 29, every 4 weeks thereafter). Can be performed at ± 3 days during first 8 weeks and ± 7 days thereafter.
- Review of concomitant medications (including steroid and anti-seizure med documentation, every week during 1st 4 weeks, every 4 weeks thereafter). Can be performed at ± 3 days during first 8 weeks and ± 7 days thereafter.
- Drug diary documentation by patient (to be collected every two weeks when patient return to get new supply of medication).
- MRI brain w/ and w/o contrast (after 4 weeks, after 8 weeks, every 8 weeks thereafter). Can be performed at ± 1 week at the after 4 weeks MRI and ± 2 weeks thereafter.
- Adverse event (AE) assessment (every week during 1st 4 weeks, every 4 weeks thereafter). Can be performed at ± 3 days during first 8 weeks and ± 7 days thereafter.
- QOL assessment after 4 weeks ± 3 days, after 8 weeks ± 1 week, after 24 week ± 2 weeks (assess for final time if patient comes off study before 24 weeks and it is > 2 weeks from previous assessment).
- Serum sample for exploratory biomarkers after 4 weeks ± 3 days.
- Pharmacokinetic assessment on day 1 (0, 30 minutes, 1, 2, 4, 6, 8 hrs from drug injection) as well as at day 8 prior to drug injections (only in first 3 patients at each dose level). (May alternatively be done on any day after the 1st week during the initial 4 weeks with no need for day 8 trough draw if done later)
- Clinical laboratory tests for:
 - CBC with differential
 - CMP

Post-Treatment Phase

The **Post-Treatment Phase** is the period after progesterone is stopped to the end-of-study (EOS) visit. The EOS visit will be scheduled 28 days after discontinuation of progesterone (window for visit can be up to 2 weeks beyond 28 days).

The following will be performed at the EOS visit:

- Brief medical history, physical exam including KPS and neurologic assessment.
- Vitals signs, weight.
- Review of concomitant medications (including steroid and anti-seizure med documentation).
- AE assessment.
- Clinical laboratory tests for CBC with differential and CMP.

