- **Partial Response (PR):** (Measurable disease only) Greater than or equal to 65% decrease under baseline in total tumor volume of all measurable lesions. No progression of non-evaluable disease (defined as progression to at least 1.5 cm^3 in volume). No new lesions. All measurable lesions and sites must be assessed using the same techniques as baseline. If there is only non-evaluable disease or no enhancing disease present at baseline, then this criteria will not apply and the case will not be considered in the N when evaluating for % of patient achieving PR.
- **Stable Disease (SD):** Does not qualify for CR, PR, or progression. The designation of SD requires a minimum of 8 weeks duration (2 assessment of stable disease from baseline at least 4 weeks apart). All measurable sites must be assessed using the same techniques as baseline. The steroid dose at the time of the scan evaluation should be no greater than the maximum dose used in the first 8 weeks from initiation of therapy.
- **Progressive Disease (PD):** 40% increase in the tumor volume of all measurable lesions over previous exam (over baseline if no decrease) using the same techniques as baseline, OR clear progression of non-evaluable disease (defined as growth to at least 1.5 cm^3 in volume), OR clear appearance of any new measurable lesion/site, OR clear clinical worsening or failure to return for evaluation due to death or deteriorating condition (unless clearly unrelated to this cancer).

Best Response: This will be calculated from the sequence of objective statuses. For patients with all disease sites assessed every evaluation period, the best response will be defined as the best objective status as measured according to the above criteria.

Pharmacokinetic Testing (Research)

Protocol Title: Pilot study of progesterone for recurrent GBM

Number of patients tested: The first three patients of a treatment dose level will be undergo pharmacokinetic testing for plasma level of progesterone.

Timing of Assessments: Pharmacokinetic samples will be obtained on day 1 of therapy. Plasma samples will

be obtained immediately prior to administration of drug and, subsequently, at 30 minutes, 1 hour, 2 hour, 4 hours, 6 hours, and 8 hours after drug injection. Additional sample will be obtained prior to the day 8 injection. (May alternatively be done on any day after the 1st week during the initial 4 weeks with no need for day 8 trough draw if done later)

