Minorities and Women: Subjects will be approximately representative of the demographics of the patient population at Emory University. This study is designed to include women and minorities, but is not designed to measure specific sex differences of intervention effects. While males and females will be recruited with no preference to gender, and based on the results of previous studies, we expect 50% of our accrual to be female. No exclusion to this study will be based on race or sex. Minorities will actively be recruited to participate. However, based on previous enrollment, we expect about 35% of subjects to be minorities.

Accrual Targets					
Ethnic Category	Sex/Gender				
	Females		Males		Total
Hispanic or Latino	2	+	2	=	4
Not Hispanic or Latino	11	+	11	=	22
Ethnic Category: Total of all subjects	13	+	13	=	26
Racial Category					
American Indian or Alaskan Native	0	+	0	=	0
Asian	1	+	1	=	2
Black or African American	2	+	2	=	4
Native Hawaiian or other Pacific Islander	0	+	0	=	0
White	10	+	10	=	20
Racial Category: Total of all subjects	13	+	13	=	26

	(A1 = A2)	(B1 = B2)	(C1 = C2)
Accrual	Total Expected		
Rate: 1-2 pts/month	Accrual: 20 Min	26 Max	
Projected Start			
Date of Study: April 1, 2021			

Inclusion Criteria

- Patients must have pathologic confirmation of a glioblastoma or gliosarcoma diagnosis at initial surgery or second or later surgery.
- Patients may have had up to two previous salvage agents administered for treatment of recurrent GBM (may be at 1st, 2nd or 3rd recurrence).
- Patients must be ≥ 18 years of age.
- Patients must be able to have MRI scans for disease follow up.
- Recurrent GBM must consist of a minimum of 1 cm³ of contrast enhancing disease on high resolution T1 post-contrast sequence as defined on pre-treatment MRI obtained within 14 days of initiating therapy. In the setting of recurrent GBM that was managed with surgery, there is no minimum disease required and the criteria for non-measurable/evaluable disease will be applied to determine imaging response (see Section 5.7).
- Patient must have the following lab values ≤ 14 days prior to registration:
 - WBC $\geq 3,000/\mu\text{L}$
 - ANC $\geq 1,500/\mu\text{L}$
 - platelet count of $\geq 75,000/\mu\text{L}$ (transfusion is not allowed within 1 week of a qualifying minimum platelet level to achieve eligibility)
 - hemoglobin ≥ 9.0 gm/dL (transfusion is allowed to reach minimum level)
 - AST/ALT $\leq 2.0\times$ UNL

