- To determine the pharmacokinetics of natural progesterone given to recurrent GBM patients by subcutaneous injection. This analysis will be performed to determine what plasma drug levels can be achieved in recurrent GBM patients with subcutaneous administration of natural progesterone and whether this is in line with what was previously determined in healthy subjects.

Dose expansion phase (Part 2):

- To determine the overall response rate (ORR) of eligible patients with recurrent GBM treated with daily subcutaneous natural progesterone. This primary analysis will be performed on all patients treated at the expansion dose (from either the dose finding or expansion phases). In particular, we will be looking for the fraction of patients that are able to maintain at least stable disease (SD), given our expectation that, for patients showing a contrast enhancing recurrence, all will continue to progress unless they are receiving an effective therapy. ORR will be reported, and an exact 95% confidence interval will be reported using the Clopper-Pearson method. There will be one interim analysis for futility that is described above that may halt enrollment before full accrual of the expansion cohort.

Secondary Objectives

Dose expansion phase (Part 2):

- To determine and compare the progression free survival of eligible patients with recurrent GBM. Patients on this study will be followed for progression free survival (PFS), which is defined from the time of pre-treatment MRI to the time of either radiographic progression or death, whichever occurs first. Both actuarial PFS curves and 24-week PFS (for expansion dose patients and all patients as separate analyses) will be estimated using the Kaplan-Meier method, and compared to matched historical controls using log-rank tests and univariate Cox proportional hazards models. The matched effects will be estimated by a Cox model with a robust variance estimator. A 95% confidence interval will be provided for 24-week PFS using the Greenwood formula to estimate the standard error.

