- To determine and compare the overall survival of eligible patients with recurrent GBM. Patients on this study will be followed for overall survival (OS) which is defined from the time of pre-treatment MRI to the time of death. Both actuarial OS curves and 24-week OS (for expansion dose patients and all patients as separate analyses) will be estimated using the Kaplan-Meier method, and compared to matched historical controls using log-rank tests and univariate Cox proportional hazards models. The matched effects will be estimated by a Cox model with a robust variance estimator. A 95% confidence interval will be provided for 24-week OS using the Greenwood formula to estimate the standard error.

Exploratory Objectives:

Dose expansion phase (Part 2):

- To determine whether progesterone receptor levels within the tumor correlates with response to daily subcutaneous natural progesterone. This will be examined for both expansion dose patient and all patients as separate analyses. Original tumor and any recurrent tumor samples will be assessed for progesterone receptor expression levels by immunohistochemistry and these results will be correlated with response assessment to determine whether there is any correlation. Progesterone receptor staining by IHC will be scored on a scale of 0-4 by standard criteria and then compared with response assessment using standard statistical tests such as two sample t-tests or Mann-Whitney U tests, where appropriate, to determine whether there is any correlation between expression level and response.
- To determine if other intrinsic tumor factors (mutations and genomic loss/gains, see **Section 5.7** for specific details) correlates with response to daily subcutaneous natural progesterone. This will be examined for both expansion dose patient and all patients as separate analyses. Each of the tumor mutational and genomic loss/gain factors will be scored and these results will be correlated with response assessment using chi-square tests or Fisher's exact tests, where appropriate.

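### PFS and OS start at the pre-treatment MRI, so 24-week PFS is usually read before the week-24 scan, and the PFS event in 15.1 conflicts with progression in 5.7

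*Combined protocol and SAP*

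**What the plan says.** **Time zero.** Section 15.1, Secondary Objectives, has PFS "defined from the time of pre-treatment MRI to the time of either radiographic progression or death, whichever occurs first" and "overall survival (OS) which is defined from the time of pre-treatment MRI to the time of death". The Section 9 inclusion criteria describe recurrent disease "as defined on pre-treatment MRI obtained within 14 days of initiating therapy". Both analysis populations in 15.1 require that study drug was received.

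**Landmark.** "Both actuarial PFS curves and 24-week PFS (for expansion dose patients and all patients as separate analyses) will be estimated using the Kaplan-Meier method". The 24 weeks therefore run from the MRI.

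**Scan timing.** Scans are counted from the start of therapy. Section 5.6 lists "MRI brain w/ and w/o contrast (after 4 weeks, after 8 weeks, every 8 weeks thereafter", which gives weeks 4, 8, 16 and 24. Footnote 7 of Section 1.3 says "To be assessed after 8 weeks of therapy ± 1 week and then every 8 weeks ± 2 weeks, thereafter", and allows other MRIs at the treating physician's discretion. Sections 1.3 and 5.6 differ on the early windows but agree on ±2 weeks at week 24.

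**Event.** Section 15.1 counts radiographic progression or death, and Section 2 refers to volumetric criteria. Progressive disease in 5.7 also includes "clear clinical worsening or failure to return for evaluation due to death or deteriorating condition", unless clearly unrelated to the cancer. Its growth criterion is "40% increase in the tumor volume of all measurable lesions over previous exam (over baseline if no decrease").

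**Comparator.** PFS and OS are compared with matched historical controls by log-rank test and Cox model. The controls' time zero, scan schedule and progression rule are not given.

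**The concern.** Three features of the definitions lengthen PFS, or can, whatever the drug does.

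- The interval from MRI to first dose cannot contain a death, because a patient who dies before dosing is never analysed.
- The 24-week estimate sits on one clock and the scan meant to inform it sits on another. Where the scan comes later, a patient who was progression-free at week 16 still counts as progression-free at 24 weeks.
- A patient who declines clinically and has no further scan has no PFS event under 15.1 until death. After the end-of-study visit this is plausible, since 5.1 leaves follow-up to the treating physician and takes progression from records retrospectively.

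PFS is a named secondary objective with a formal comparison. With about 20 patients at the expansion dose, a shift of 10 percentage points is two patients.

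**Working it through.** The plan gives no assumed PFS rate, hazard ratio or event count, so there is no figure of its own to reproduce. The medians below are assumptions.

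**1. Clock.** PFS time as written = time from first dose + gap, with a gap of 0 to 14 days. The same holds for OS.

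**2. Where the week-24 scan falls on the MRI clock.** Nominal week = 24 + gap/7, with ±2 weeks.

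| Gap (days) | Nominal week | Range |
|---|---|---|
| 0 | 24 | 22 to 26 |
| 7 | 25 | 23 to 27 |
| 14 | 26 | 24 to 28 |

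Assume the gap g is uniform on 0 to 14 days and the window deviation uniform on −14 to +14 days. The chance that the scan falls by 24 weeks is the mean of (14 − g)/28 = (14 − 7)/28 = 0.25. The other 75% fall later. The week-16 scan always falls in time, at week 18 + 2 = 20 at the latest.

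**3. Effect on 24-week PFS.** Assume exponential progression from first dose, detected only at scheduled scans, so S(t) = 0.5^(t/median).

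- *As written:* 75% of patients are read from week 16. The other 25% are read from week-24 scans done early, on average at week 22.67 of therapy (under step 2, days early has density proportional to d on 0 to 14, mean 9.33 days). PFS ≈ 0.75 × S(16) + 0.25 × S(22.67).
- *Clock at first dose:* half the week-24 scans are still late because of the window, and the early half average week 23. PFS ≈ 0.5 × S(16) + 0.5 × S(23).
- *Scans also given their nominal week:* everyone is read from the week-24 scan. PFS ≈ S(24).

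| Median (weeks) | S(16) | S(22.67) | S(23) | As written | Clock at first dose | Nominal week too |
|---|---|---|---|---|---|---|
| 8 | 0.250 | 0.140 | 0.136 | 0.223 | 0.193 | 0.125 |
| 10 | 0.330 | 0.208 | 0.203 | 0.299 | 0.266 | 0.189 |
| 12 | 0.397 | 0.270 | 0.265 | 0.365 | 0.331 | 0.250 |

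Simulation with the Section 1.3 windows agrees: 22.3%, 30.0% and 36.6% as written. Moving the clock accounts for about 3 points. The nominal-week assignment accounts for a further 7 to 8 points (0.193 − 0.125 = 0.068; 0.331 − 0.250 = 0.081).

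**4. Sensitivity.** If progression starts at the MRI, the as-written values are about 20%, 28% and 34%. If instead 30 to 50% of progressions are caught by unscheduled scans (assumption), they are 18 to 20%, 25 to 27% and 32 to 34%.

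**5. Event definition.** Suppose 10 to 30% of progressions are first seen clinically (assumption; MRI clock, 14-day gap, nominal scan days). Counting them when they occur lowers 24-week PFS from 24.9% to 23.9% or 21.9% (median 8 weeks), and from 39.7% to 38.5% or 36.1% (median 12 weeks). That is about 1 to 3.5 points.

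**6. Growth reference in 5.7.** For a tumor that never shrank the reference is baseline, so the rule matches a smallest-volume rule: 10, 12, 13.5, 16 cm³ is progression at 16 (+60%) under both. After shrinkage the text can be read two ways. Take 10, 9, 12.5, 17.4, 24.2 cm³, with steps of +39% after the fall to 9.

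- If no decrease means never below baseline, the previous exam stays the reference. Progression is never called on volume, though 24.2/9 = 2.7.
- If it means no decrease since the previous exam, then at 17.4 the reference is baseline. 17.4/10 is +74%, which is progression.

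**The case against.** **The MRI clock is coherent for PFS.** Volume is compared with the baseline MRI, so growth during the gap counts toward progression. A first-dose clock charges that growth to treated time. This stands as a cost of the change, and step 4 shows the smaller figures when progression starts at the MRI. It does not help OS, where the gap is simply guaranteed survival.

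**Most of the 10-point difference is not the clock.** This is correct. A reader might attribute all of it to the early start, but the clock gives about 3 points. The rest comes from reading the landmark before the week-24 scan, and scan windows cause that on any clock. It is why moving time zero alone is not enough.

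**A reader might infer that every rule favors progesterone.** The documents do not support that. The controls' time zero, scans and progression rule are unstated. If they match, the definitions need not bias the comparison.

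**A reader might also infer that growth is always judged against the previous scan.** The parenthesis about baseline in 5.7 rules that out. Only tumors that have shrunk are affected, and there the text is ambiguous.

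**PFS is secondary in a small pilot.** True, and this limits the consequences. The plan still commits to a formal comparison.

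**Conclusion.** The point holds for time zero, the landmark and the event definition. The MRI clock adds 0 to 14 days to OS and up to 14 days to PFS in patients selected for having been dosed. With uniform gaps and windows, about three quarters of week-24 scans come too late to inform the 24-week estimate. It then reads about 22%, 30% and 37% where status at the week-24 scan would give 12.5%, 19% and 25%. Those figures assume exponential progression from first dose with medians of 8, 10 and 12 weeks, detected only at scheduled scans. The as-written values are lower if progression starts at the MRI or unscheduled scans detect it.

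Sections 15.1 and 2 contradict 5.7 on clinical progression. The comparison with historical controls is biased to the extent that their definitions differ, and neither size nor direction can be established from the documents. The growth reference in 5.7 is an ambiguity to clarify, not a demonstrated lengthening of PFS in all patients.

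**What to change.** In 15.1:

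- Start PFS and OS at first dose.
- Take 24-week PFS from the week-24 scan by assigning each scheduled scan its nominal week.
- Reconcile 15.1 and Section 2 with 5.7, so that the PFS event is progressive disease per 5.7, including clinical progression, or death.
- Apply the same time zero (start of therapy) and event definition to the controls as far as their data allow, and state where they cannot be matched.

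Separately, state which reference volume the PFS analysis uses after shrinkage. Make this an analysis definition in 15.1. Protocol-specified progression is also a reason to stop treatment under 8.1, so the stopping rule in 5.7 and 8.1 is for the sponsor to reconcile.

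For trial patients this is wording and needs no new data. Aligning the controls depends on data the documents do not describe. Reported PFS and OS become somewhat shorter, and growth between the baseline MRI and first dose falls within treated time. The changes should be made before outcomes are analysed.

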
To determine and compare the progression-free survival of eligible patients with recurrent GBM compared with matched historical controls treated with a range of standard therapies.To determine and compare the overall survival of eligible patients with recurrent GBM compared with matched historical controls treated with a range of standard therapies.	
Progression-free Survival (PFS) using protocol specified volumetric progression criteria.Overall Survival (OS)
Tertiary/Exploratory	

To determine whether progesterone receptor levels within the tumor correlates with response to daily subcutaneous natural progesterone.To determine if other intrinsic tumor factors (mutations and genomic loss/gains, see Section 5.7 for specific details) correlates with response to daily subcutaneous natural progesterone.To determine if the absolute values or changes in the level of serum biomarkers (see Section 5.7 for specific biomarkers) correlates with response to daily subcutaneous natural progesterone.To determine the quality-of-life (QOL) by validated instruments of eligible patients with recurrent GBM treated with daily subcutaneous natural progesterone and assess whether this differs from historical controls.	
Levels of progesterone receptor expression by immunohistochemistry.Specified intrinsic tumor factors (genetic/epigenetic changes, see Section 5.7).Absolute levels/changes in specified serum biomarkers (see Section 5.7) before and 4 weeks after treatment with progesterone.QOL assessment by the EORTC Quality of Life Questionnaire-Core 30/Brain Cancer Module-20 (EORTCQLQ30/ BN20) and M. D. Anderson Symptom Inventory Brain Tumor Module (MDASI-BT).

3. Background

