Patients with progressive disease (PD) per protocol-specified criteria but with otherwise stable or improved performance and clinical status may continue to be treated in the event of a perceived benefit per Investigator. Patients who are tolerating the drug with stable disease (SD) or better after 24 weeks of therapy may be considered for compassionate use continuation on a case-by-case basis after discussions between the patient, treating physician and the study supporter (IBSA Institut Biochimique SA, Lugano, Switzerland). It is at the discretion of the Investigator to continue treating patients in this circumstance as long as IBSA agrees to continue to provide drug until unacceptable toxicity, disease progression or patient withdrawal. Followup evaluations under these circumstances will be considered standard-of-care at the discretion of the patient's treating physician.

The EOT period would last for 4 weeks after drug discontinuation at which point the end-of-study (EOS) visit would occur where final Adverse Event (AE) documentation and other study-required assessments are performed. Further assessment of progression or death for determination of PFS and OS will be based on review of records obtained after this point on a retrospective basis where additional treatments and followup intervals will be at the discretion of the patient's treating physician.

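### The PFS comparison with historical controls dates progression at the scan but nothing aligns scan timing, so the hazard ratio and p-value mix drug effect with MRI schedule, in an unknown direction

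*Combined protocol and SAP*

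**What the plan says.** Section 15.1 (Secondary Objectives) takes PFS as "defined from the time of pre-treatment MRI to the time of either radiographic progression or death, whichever occurs first". The curves and the 24-week estimate are to be "compared to matched historical controls using log-rank tests and univariate Cox proportional hazards models". For the matching it adds: "The matched effects will be estimated by a Cox model with a robust variance estimator".

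Section 2 lists the endpoint as "Progression-free Survival (PFS) using protocol specified volumetric progression criteria". Section 5.7 makes the main volumetric criterion a "40% increase in the tumor volume of all measurable lesions over previous exam (over baseline if no decrease"), which can only be established on an MRI.

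The trial's scan times are fixed during treatment. Section 5.6 lists "MRI brain w/ and w/o contrast (after 4 weeks, after 8 weeks, every 8 weeks thereafter"). The Section 1.3 table has an MRI at day 29, and its footnote on later MRIs reads "To be assessed after 8 weeks of therapy ± 1 week and then every 8 weeks ± 2 weeks, thereafter". After the end-of-study visit, Section 5.1 leaves the timing open: "additional treatments and followup intervals will be at the discretion of the patient's treating physician".

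The controls are described only as matched and as treated with a range of standard therapies. Their number, source, scan schedule and progression criteria are not stated. Section 15.1 has no interval-censored method, no common scan grid and no sensitivity analysis for scan timing.

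**The concern.** A progression that occurs at week 2 is recorded at week 4 in a trial patient. In a control whose first scan was at week 8, the same progression is recorded at week 8. The log-rank and Cox analyses treat those recorded dates as the event times. Their null hypothesis is therefore equal progression together with equal scan timing, whereas the stated objective concerns progression alone. The robust variance allows for matching in the standard error and leaves the event dates as they are.

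This matters most when the disease progresses on the scale of the scan interval. Two treatments with identical true PFS can then give a hazard ratio away from 1, a real benefit can be shrunk, or an apparent benefit can be produced. Without the controls' schedule, neither the sponsor nor a reader could separate a drug effect from a schedule effect.

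**Working it through.** **Inputs from the documents.** Trial scans at weeks 4, 8, 16, 24 and so on, with windows of ±3 days, ±1 week and then ±2 weeks (Section 1.3; Section 5.6 gives wider windows for the first two scans). 20 patients at the expansion dose (Section 15.1). No alpha, power, effect size, event count or control number is stated for PFS, so there is no planned figure to reproduce.

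**Assumptions.** Exponential time to progression with the same median in both groups; control scans every 4, 6, 8 or 12 weeks; two-sided 5% log-rank test.

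**Step 1: the mechanism by arithmetic.** Take exact scan days counted from time zero and let S(t) = 2^(−t/m), where m is the median. With scans every d weeks, the mean recorded time is d / (1 − S(d)). The trial schedule is the 8-weekly grid plus a week-4 scan, so its mean is 8 / (1 − S(8)) − 4 × (1 − S(4)).

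For m = 8 weeks, S(4) = 0.7071, S(6) = 0.5946, S(8) = 0.5 and S(12) = 0.3536:

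| Schedule | Calculation | Mean recorded time (weeks) |
|---|---|---|
| Trial | 16.00 − 4 × 0.2929 | 14.83 |
| Every 4 weeks | 4 / 0.2929 | 13.66 |
| Every 6 weeks | 6 / 0.4054 | 14.80 |
| Every 8 weeks | 8 / 0.5 | 16.00 |
| Every 12 weeks | 12 / 0.6464 | 18.56 |

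True PFS is the same in every row. Against 8- or 12-weekly controls the trial looks worse, against 6-weekly controls about equal, and against 4-weekly controls better.

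The gap to 8-weekly controls is 4 × (1 − S(4)) weeks. It depends on the pace of the disease:
- m = 3.4 weeks (20% progression-free at week 8): 4 × 0.553 = 2.2 weeks, on a control mean of 8 / 0.80 = 10.0.
- m = 8 weeks: 4 × 0.293 = 1.2 weeks, on 16.0.
- m = 12 weeks: 4 × 0.206 = 0.8 weeks, on 21.6.

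**Step 2: effect on the test.** Simulated with no true difference, 20 trial patients, 20 to 40 controls, the trial's own windows and an assumed ±1 week for control scans. The nominal rate is 2.5% in each direction.

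| Control scans | Median PFS (weeks) | Result |
|---|---|---|
| Every 8 weeks | 8-12 | drug significantly worse: about 5-7% |
| Every 8 weeks | 3.4-5.3 | drug significantly worse: 8-38% |
| Every 12 weeks | 3.4-12 | drug significantly worse: about 6-64% |
| Every 6 weeks | 8 or more | near nominal |
| Every 4 weeks | 3.4-12 | drug significantly better: about 4-6% |

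**Step 3: effect on the hazard ratio.** With scan windows, 20 to 60 controls, medians of 6 to 16 weeks and a true hazard ratio of 1.0, the mean estimates are:
- controls on the trial schedule: 0.99-1.04
- every 4 weeks: 0.88-0.95
- every 6 weeks: 0.97-1.07
- every 8 weeks: 1.04-1.26
- every 12 weeks: 1.12-1.57

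With a true hazard ratio of 0.8, 60 controls and 8-weekly control scans, the mean estimate is 0.94 (median 6 weeks) or 0.89 (median 8 weeks). On a common grid it is 0.83.

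**Step 4: do the remedies work?** Dating week-4 findings at week 8, with 8-weekly controls (20 or 60) and medians of 6 to 16 weeks, brings the rate of significantly worse from 3.0-14.4% back to 2.5-3.7%. The mean hazard ratio goes from 1.04-1.25 to 0.99-1.03. An unmatched Weibull interval-censored likelihood-ratio test rejected in about 4-9% of runs against a two-sided 5% (250 runs per case). Matching was not simulated in either check.

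**The case against.** The controls' scan schedule is unknown, so calling the week-4 MRI extra already assumes something about them. A reader might infer that the plan is biased against progesterone. The documents do not support a direction: the bias nearly vanishes with 6-weekly controls at medians of 8 weeks or more, and reverses with 4-weekly ones. This stands.

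A reader might also take the 10% in the futility paragraph of Section 15.1 as the controls' 8-week PFS and conclude that false rejection exceeds 90%. That figure is a response rate for ineffective therapies, whereas the controls received standard therapies. Response here also includes stable disease, which under Section 5.7 needs two assessments at least 4 weeks apart and a steroid limit, so failing to meet it is not the same as a PFS event. The plan states no control PFS.

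Large rejection rates also depend on scans falling on exact days. With 8-weekly controls and a median of 3.4 weeks, 58% and 81% significantly worse (20 and 40 controls) fall to 26% and 38% once windows are applied. Events dated off the scan calendar, such as deaths, generally shrink the effect further. Eligibility includes first recurrence, resected disease and a life expectancy of at least 12 weeks, so the shortest medians may not apply.

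Finally, PFS is secondary in a pilot, and no alpha, power or decision rests on it; the futility rule uses response. The planned 24-week PFS estimate should be less exposed to a week-4 scan if both groups were scanned near week 24, although the ±2-week window falls on that landmark. These points limit size and priority. They do not supply the missing alignment.

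**Conclusion.** The point holds as a bias of unknown direction. As written, the PFS hazard ratio and p-value combine any drug effect with any difference in scan timing, and the plan has no means of separating them. The likely size runs from negligible (controls scanned on the trial schedule, or 6-weekly with slower disease) to serious (12-weekly controls with fast disease).

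The simulated figures rest on exponential progression, all progression found by scan, the Section 1.3 windows, and assumed control numbers, schedules and windows. They show a range and do not predict what this trial will see. The point is worth correcting because the remedy is cheap, but it does not threaten a primary endpoint. OS is unaffected, since death dates do not depend on scans.

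**What to change.** In Section 15.1, under PFS:
- For every patient in both groups, record the last scan without progression and the first scan (or death) with progression.
- Keep the planned log-rank and Cox comparison, and add an interval-censored proportional hazards analysis. A common-grid analysis is a simpler alternative, for example dating week-4 findings at week 8 if controls were scanned every 8 weeks.
- Report the controls' actual scan schedule beside the result.
- Interpret the PFS comparison only where the planned and added analyses agree.
- Leave the OS analysis unchanged.

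An added analysis is preferable to a replacement, because an interval-censored model with variance adjusted for matching has not been checked at this sample size.

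The cost is some plan wording and one more scan date to abstract per patient, which assumes that the controls' scan records can be retrieved. No visits or patients are added. The interval-censored model is less familiar, and its p-values are approximate at this size.
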